6.6.1.1 Enfortumab Vedotin-Related Skin Reactions (Rash and SCAR)

Low to moderate levels of Nectin-4 are also expressed on normal tissues, including skin keratinocytes, sweat glands and hair follicles; thus, skin reactions are anticipated events. As such, skin reactions are AEs of interest in all clinical studies with enfortumab vedotin.

A cumulative review of post-marketing safety data from 18 Dec 2019 (the approval date of enfortumab vedotin in the US) through 17 Dec 2022 identified reports of adverse reactions. In enfortumab vedotin monotherapy studies of urothelial carcinoma, 52.3% participants experienced at least 1 TEAE of rash and 3.8% experienced serious rash events. SAEs of rash included rash maculo-papular (1.1%), rash (0.6%), dermatitis bullous (0.5%), drug eruption (0.4%), rash vesicular (0.3%), Stevens-Johnson syndrome (SJS) (0.2%), toxic skin eruption (0.2%), and blister, eczema, erythema, erythema multiforme, rash pruritic, and symmetrical drug-related intertriginous and flexural exanthema (SDRIFE) (0.1% each).

SCAR events accounted for 22.3% of TEAEs; 1.8% of participants experienced serious SCAR, while the majority had grade 1 or 2 as the worst grade. The SAEs of SCAR included dermatitis bullous (0.5%), drug eruption (0.4%), SJS (0.2%), toxic skin eruption (0.2%), and blister, conjunctivitis, dermatitis exfoliative, erythema multiforme, stomatitis, and SDRIFE (0.1% each).

Subjects should be informed that rash and severe skin reactions have occurred after administration of EV, and to contact the Investigator immediately if they have signs and symptoms of skin reactions, oral mucosal and ocular abnormalities including mucositis or conjunctivitis. Starting in the first cycle and throughout treatment, closely monitor subjects for skin reactions. For mild to moderate skin reactions, consider appropriate treatment, such as topical corticosteroids and antihistamines as clinically indicated. For recommendations regarding dose modifications for skin reactions due to EV, refer to [Table 8].

6.6.1.2 Management of Pneumonitis/Interstitial Lung Disease related to Enfortumab Vedotin

Severe, life-threatening or fatal pneumonitis/ILD have occurred in subjects receiving enfortumab vedotin. Monitor subjects for signs and symptoms indicative of pneumonitis/ILD such as hypoxia, cough, dyspnea or interstitial infiltrates on radiologic exams. For all subjects, including subjects with asymptomatic/grade 1 pneumonitis/ILD, clinical monitoring and supportive measures consistent with local medical guidelines should be followed as appropriate throughout the study. Medical intervention per standard of care should be considered for grade ≥ 2 events (e.g., corticosteroids initial dose of 1-2 mg/kg/day prednisone or equivalent followed by a taper). For recommendations regarding dose modifications for pneumonitis/ILD due to enfortumab vedotin, refer to [Table 8].

6.6.1.3 Management of Hyperglycemia

Investigators should monitor blood glucose levels and are advised to perform additional assessments if any symptoms of hyperglycemia are observed, including a thorough evaluation for infection. In addition, if steroids are used to treat any other condition, blood glucose levels may require additional monitoring. If elevated blood glucose levels are observed, subjects should be treated according to local standard of care and referral to endocrinology may be considered.

Subjects, especially those with a history of or ongoing diabetes mellitus or hyperglycemia, should be advised to immediately notify their physician if their glucose level becomes difficult to control or if they experience symptoms suggestive of hyperglycemia such as frequent urination, increased thirst, blurred vision, fatigue, and headache.

Subjects who enter the study with an elevated HbA1c ($\geq 6.5\%$) at baseline should be referred to an appropriate provider during cycle 1 for glucose management. Blood glucose should be checked prior to each dosing and dose should be withheld for blood glucose > 250 mg/dL (13.9 mmol/L) (grade 3 or higher). Dosing may continue once the subject's blood glucose has improved to \leq grade 2 and subject is clinically and metabolically stable. Blood glucose > 500 mg/dL (27.8 mmol/L) (grade 4) considered related to enfortumab vedotin requires treatment discontinuation. If a subject experiences new onset diabetes mellitus, evaluate subjects with a metabolic panel, urine ketones, HbA1c, and C-peptide to assess for new onset diabetes.

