Dose interruptions for any enfortumab vedotin associated toxicities are permitted at the discretion of the investigator. Dose interruptions may last up to 8 weeks (2 cycles) for subjects in cohorts 1 to 8 and up to 6 weeks (2 cycles) for subjects in cohort 9. Dose interruptions for subjects who are deriving clinical benefit from treatment may be extended beyond 8 weeks (cohorts 1 to 8) or 6 weeks (cohort 9) after consultation with the medical monitor on a monthly basis, if the subject's toxicity does not otherwise require permanent discontinuation. During dose interruptions, disease assessments must continue to be performed at the protocol-specified frequency and disease status must remain at least SD per RECIST v1.1. If dose interruption is continuous > 6 months, the subject's study treatment will be permanently discontinued.

Refer to Section 6.6.1 [Table 7] and [Table 8] for dose modification recommendations for enfortumab vedotin.

Name:

Pembrolizumab (cohort 9 only)

Dose, Mode of Administration and Dose Modification:

Pembrolizumab injection is a sterile, preservative-free, clear to slightly opalescent, colorless to slightly yellow solution that requires dilution for IV infusion. Each vial contains 100 mg of pembrolizumab in 4 mL of solution. Each 1 mL of solution contains 25 mg of pembrolizumab and is formulated in L-histidine (1.55 mg), polysorbate 80 (0.2 mg), sucrose (70 mg), and Water for Injection, United States Pharmacopeia (USP). Pembrolizumab will be administered as a dose of 200 mg using a 30-minute intravenous infusion on day 1 of each 3-week cycle, approximately 30 minutes after completion of the enfortumab vedotin administration. Sites should make every effort to target infusion timing to be as close to 30 minutes as possible. However, given the variability of infusion pumps from site to site, a window between -5 minutes and + 10 minutes is permitted (i.e., infusion time is 30 minutes (-5 min/+10 min)).

The pharmacy manual contains specific instructions for the preparation of the pembrolizumab infusion and administration of infusion solution.

Refer to Section 6.6.2 [Table 9] and [Table 10] for dose modification recommendations for pembrolizumab.

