6.6 Dose Modification

6.6.1 Enfortumab Vedotin

For all cohorts, dose reduction to 1, 0.75 or 0.5 mg/kg will be allowed depending on the type and severity of toxicity. Subjects requiring a dose reduction may be re-escalated by 1 dose level (i.e., subjects reduced to 0.75 mg/kg may only be re-escalated to 1 mg/kg) provided the toxicity does not require study drug discontinuation and has returned to baseline or \leq grade 1. If the toxicity recurs, re-escalation will not be permitted. Subjects with \geq grade 2 corneal AEs will not be permitted to dose re-escalate.

Dose modification recommendations for enfortumab vedotin associated toxicity are presented in [Table 7] and [Table 8].

Dose interruptions for any enfortumab vedotin associated toxicities are permitted at the discretion of the investigator. Dose interruptions may last up to 8 weeks (2 cycles) for subjects in cohorts 1 to 8 and up to 6 weeks (2 cycles) for subjects in cohort 9. Dose interruptions for subjects who are deriving clinical benefit from treatment may be extended beyond 8 weeks (cohorts 1 to 8) or 6 weeks (cohort 9) after consultation with the medical monitor on a monthly basis, if the subject's toxicity does not otherwise require permanent discontinuation. During dose interruptions, disease assessments must continue to be performed at the protocol-specified frequency and disease status must remain at least SD per RECIST v1.1. If dose interruption is continuous > 6 months, the subject's study treatment will be permanently discontinued.

For all cohorts, if toxicities are present on day 1 of any cycle and enfortumab vedotin cannot be administered, then the start of the cycle may be delayed.

For cohorts 1 to 8, if toxicities are present on days 8 or 15 of any cycle and require the dose to be held > 3 days, then the dose(s) must be eliminated (skipped), rather than delayed. If a subject only receives the day 1 dose and days 8 and 15 doses need to be eliminated (skipped),

then the subject could resume the next cycle as early as day 22 (new day 1), if the toxicity has resolved by that time.

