Continue at same dose level.	Continue at same dose level. For grade 2 thrombocytopenia withhold dose until toxicity is \leq grade 1 or has returned to baseline, then resume treatment at the same dose level.	Withhold dose until toxicity is \leq grade 1 or has returned to baseline, then resume treatment at the same dose level or consider dose reduction by 1 dose level. Transfusions or growth factors may be used as indicated per institutional guidelines.	Withhold dose until toxicity is \leq grade 1 or has returned to baseline, then reduce dose by 1 dose level and resume treatment or discontinue at the discretion of the investigator. Transfusions or growth factors may be used as indicated per institutional guidelines. For anemia, treatment discontinuation should be strongly considered.
*Hematologic toxicity refers to anemia, thrombocytopenia, neutropenia and febrile neutropenia.			

Table 8 Recommended Dose Modifications for Enfortumab Vedotin Associated Non-hematologic Toxicity

Toxicity	Grade			
Skin reactions	Any grade			
	For suspected SJS, suspected TEN or bullous lesions, immediately withhold EV and refer the subject to a dermatologist/specialist for diagnosis and specialized care. For confirmed SJS or TEN, permanently discontinue treatment. If SJS or TEN is ruled out, see recommendations provided below for skin reactions.			
	Grade 1	Grade 2	Grade 3	Grade 4
	Continue at same dose level. For grade 1 rash or skin reactions, the subject may continue at the same dose level. See also [Section 6.6.1.1] for recommended management of rash.	Continue at same dose level. For worsening rash or skin reactions or skin reactions with concomitant fever, withhold enfortumab vedotin until toxicity is \leq grade 1 or has returned to baseline, and then resume treatment at the same dose level or consider dose reduction by 1 level. Consider referral of the subject to a dermatologist/specialist for diagnosis and specialized care.	Withhold enfortumab vedotin until toxicity is \leq grade 1 or has returned to baseline, and then resume treatment at the same dose level or consider dose reduction by 1 level. Consider referral of the subject to a dermatologist/specialist for diagnosis and specialized care. Subjects who have confirmed SJS or recurrent \geq grade 3 rash events should have therapy permanently discontinued.	For grade 4 AEs, discontinue treatment. ² For confirmed SJS or TEN, or grade 4 rash or skin reactions, permanently discontinue treatment.

Toxicity	Grade			

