Ocular	Grade 1	Grade 2	Grade 3	Grade 4
	If ocular symptoms and/or changes in vision are identified, the subject should be evaluated with an ophthalmologic exam. ¹	
Withhold dose until toxicity is \leq grade 1 or has returned to baseline, and then resume treatment at the same dose level. For the second occurrence of grade 2 corneal AEs withhold dose until toxicity is \leq grade 1, and then reduce the dose by 1 dose level and resume treatment.
 
If ocular symptoms and/or changes in vision are identified, the subject should be evaluated with an ophthalmologic exam.¹
	
Discontinue treatment at the discretion of the investigator.
 
If ocular symptoms and/or changes in vision are identified, the subject should be evaluated with an ophthalmologic exam.¹
	For grade 4 AEs, discontinue treatment.
Neuropathy	Grade 1	Grade 2	Grade 3	Grade 4
	Continue at same dose level.	Withhold dose until toxicity is \leq grade 1 or has returned to baseline, and then resume treatment at the same dose level. For the second occurrence of grade 2 neuropathy withhold dose until toxicity is \leq grade 1, and then reduce the dose by 1 dose level and resume treatment.	Discontinue treatment at the discretion of the investigator.	For grade 4 AEs, discontinue treatment.

Toxicity	Grade			
	Grade 1	Grade 2	Grade 3	Grade 4
Gastrointestinal	Continue at same dose level.	Continue at same dose level.	Withhold dose until toxicity is \leq grade 1 or has returned to baseline, then resume treatment at the same dose level or consider dose reduction by 1 dose level. ²	For grade 4 AEs, discontinue treatment. grade 4 vomiting and/or diarrhea that improves to \leq grade 2 within 72 hours with supportive management does not require discontinuation.
Hyperglycemia	Continue at same dose level.	Continue at same dose level.	Withhold study treatment. Resume treatment once hyperglycemia/elevated blood glucose has improved to \leq grade 2 and subject is clinically and metabolically stable.	Withhold enfortumab vedotin treatment and undertake a full evaluation of the hyperglycemia to determine the underlying diagnosis. Once blood glucose returns to \leq grade 2, drug dosing may resume with close monitoring after consultation with the medical monitor.

Toxicity	Grade			

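### Protocol Section 6.6.1.3 requires discontinuation for related grade 4 hyperglycemia, but the Table 8 grade 4 cell lets dosing resume, with no causality condition and no reference to 6.6.1.3

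*Protocol*

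**What the plan says.** Section 6.6.1.3 (Management of Hyperglycemia) withholds enfortumab vedotin when glucose exceeds 250 mg/dL (13.9 mmol/L, grade 3 or higher). It lets dosing continue once glucose is at or below grade 2 and the subject is stable. It then sets a separate rule for glucose above 500 mg/dL (27.8 mmol/L): "grade 4) considered related to enfortumab vedotin requires treatment discontinuation". Section 8.1 defines discontinuation from treatment as permanent.

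Table 8 in Section 6.6.1 is titled "Recommended Dose Modifications for Enfortumab Vedotin Associated Non-hematologic Toxicity". For grade 3 hyperglycemia it withholds treatment until glucose is at or below "grade 2 and subject is clinically and metabolically stable". For grade 4 it withholds enfortumab vedotin and asks the site to "undertake a full evaluation of the hyperglycemia to determine the underlying diagnosis". After a return to grade 2 or lower, "drug dosing may resume with close monitoring after consultation with the medical monitor".

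Section 6.6.1 states: "Dose modification recommendations for enfortumab vedotin associated toxicity are presented in [Table 7] and [Table 8". The synopsis states: "Refer to Section 6.6.1 [Table 7] and [Table 8] for dose modification recommendations for enfortumab vedotin". Neither names Section 6.6.1.3.

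**The concern.** For a grade 4 event judged related to enfortumab vedotin, one text ends enfortumab vedotin treatment and the other permits it to restart. The synopsis and Section 6.6.1 send sites to the tables for dose modification. A site that does so could re-dose a subject whom Section 6.6.1.3 says must stop.

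Section 2.2.2 lists hyperglycemia among the important identified risks of enfortumab vedotin. If the 6.6.1.3 rule counts as a withdrawal criterion, re-dosing would also meet major deviation category PD2 in Section 10.3, even though the site had followed the table.

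**Working it through.** No arithmetic applies. The check is a comparison of the two texts.

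| Point | Section 6.6.1.3 | Table 8, hyperglycemia row |
|---|---|---|
| Immediate action, grade 3 or higher | Withhold | Withhold |
| Resuming after grade 3 | Grade 2 or lower and stable | Same |
| Resuming after grade 4, related | Not allowed; discontinuation required | Allowed at grade 2 or lower, with monitoring, after medical monitor consultation |
| Resuming after grade 4, not related | Grade 2 or lower and stable (general rule) | Allowed on the same terms as a related event; stability not mentioned |
| Causality condition for grade 4 | Yes | None in the cell |
| Reference to the other text | None | None |

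**Do related events fall within the cell?** Yes. The table title and the pointer in Section 6.6.1 both limit Table 8 to toxicity associated with enfortumab vedotin. The cell therefore takes in the very events for which 6.6.1.3 requires a stop.

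**Does anything else settle it?**

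- Two clauses in Section 6.6.1 give way to required discontinuation. One concerns dose re-escalation and the other extended interruption. Neither governs resumption after grade 4 hyperglycemia.
- Section 6.7 tells the investigator to follow the most conservative guideline, but only for skin reactions.
- Table 8 footnote 2 covers grade 3 and 4 laboratory abnormalities. As the text reads, it is not attached to the hyperglycemia cell.
- Table 9 governs pembrolizumab only. Section 8.1 lists unacceptable toxicity without defining it for glucose.

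**Cross-references.** Three toxicities have both a management section and a named Table 8 row: skin reactions (6.6.1.1), pneumonitis/ILD (6.6.1.2) and hyperglycemia (6.6.1.3). The first two sections refer the reader to Table 8 and 6.6.1.3 does not, so 2 of 3 carry the link. The skin row also points back: "See also [Section 6.6.1.1] for recommended management of rash". Between 6.6.1.3 and the hyperglycemia row there is a reference in 0 of 2 directions. These counts locate the missing link; they do not measure risk.

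**Frequency.** Section 2.5.1 reports hyperglycemia in the cisplatin-ineligible urothelial cohort of EV-103: 11 subjects (14.5%) on the combination and 8 (11.0%) on enfortumab vedotin alone. These figures are not restricted to grade 4, and the documents give no rate for related grade 4 events.

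**The case against.** The best defense is that the two texts can be combined. Section 6.6.1.3 is specific and mandatory. Table 8 is headed as recommended, and its cell only permits resumption, after an evaluation of the cause and a consultation. A permission does not cancel a requirement, so the intended sequence may be to evaluate, stop if related, and otherwise resume. Investigators already record a yes/no causality judgment for every adverse event (Section 12.4.3). This reading is reasonable and probably intended. But the cell never says that the evaluation decides whether dosing may resume, and the medical monitor consults the same conflicting text.

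Some narrower objections have force:

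- The stability condition missing from the grade 4 cell is supplied by the general sentence in 6.6.1.3, which covers grade 3 or higher. That holds only for someone who reads both texts.
- The cross-reference pattern is supporting evidence only. Sections 6.6.1.1 and 6.6.1.2 point to Table 8 for their dosing rules, whereas 6.6.1.3 states its own. The infusion reaction section (6.6.1.4) has no pointer either, though it has no named row in Table 8; counting it gives 2 of 4. The pneumonitis/ILD row does not point back to its section.
- The synopsis names Section 6.6.1, the parent of 6.6.1.3, so a careful reader could reach the rule.
- Nothing in the documents shows which rule the sponsor meant to control.

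These points limit the weight of the finding but do not remove the conflict.

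**Conclusion.** The inconsistency is real and should be fixed. The same event, grade 4 hyperglycemia considered related to enfortumab vedotin, must lead to discontinuation under Section 6.6.1.3 and may lead to re-treatment under Table 8.

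The consequence is limited. Dosing is withheld at once under both texts, a medical monitor is consulted before any restart under Table 8, and the grade 3 rule agrees in both places. What remains is re-dosing after recovery from a related grade 4 event, in any cohort. The size in subjects is unknown. The primary endpoint is unaffected, and the SAP discontinuation summaries (Section 6.5.1) report the action actually taken and should continue to do so.

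The conclusion rests on the plain wording of both texts and on the absence of any statement about which prevails. The direction of the fix assumes that the mandatory text controls.

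**What to change.** Amend the Table 8 grade 4 hyperglycemia cell along these lines: *Withhold enfortumab vedotin and evaluate. If considered related to enfortumab vedotin, permanently discontinue enfortumab vedotin (see Section 6.6.1.3). Otherwise dosing may resume at grade 2 or lower, when clinically and metabolically stable, after consultation with the medical monitor.* End Section 6.6.1.3 with a reference to Table 8.

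The wording stops enfortumab vedotin for any event judged related to it, including one attributed to both drugs in cohort 9. It names enfortumab vedotin only, because Sections 6.6.2.1 and 8.1 let pembrolizumab continue when toxicity is clearly due to enfortumab vedotin alone. Re-treatment stays open when another cause is found, including hyperglycemia with beta-cell failure in cohort 9, for which Table 9 governs pembrolizumab. The sponsor should confirm the intent; if Table 8 was meant to control, Section 6.6.1.3 must change instead.

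The cost is one cell, one cross-reference and a site notice, carried in the next amendment with the signatures and IRB/IEC approval set out in Section 12.1.3. No stand-alone amendment and no SAP change are needed. The planned study period runs to about 1Q2026, so if no further amendment is due, a notice restating the existing 6.6.1.3 requirement would carry the practical effect. The downside is that a recovered subject who is benefiting cannot restart enfortumab vedotin after a related event, which 6.6.1.3 already requires.

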6.6.1.4 Management of Enfortumab Vedotin Infusion Related Reactions

An IRR may occur during the infusion of study treatment. The infusion should be administered at a site properly equipped and staffed to manage anaphylaxis should it occur. All supportive measures consistent with optimal subject care should be given throughout the study according to institutional standards. Supportive measures may include administering medications for IRRs.

Subjects who experience an IRR may be premedicated for subsequent infusions. Premedication may include pain medication (e.g., acetaminophen or equivalent), an antihistamine (e.g., diphenhydramine hydrochloride), and a corticosteroid administered approximately 30 to 60 minutes prior to each infusion or according to institutional standards. Should a subject experience IRRs in the setting of premedication, continued treatment with enfortumab vedotin must be discussed with the medical monitor prior to the next planned dose.

If anaphylaxis occurs, study treatment administration should be immediately and permanently discontinued.

6.6.2 Pembrolizumab

6.6.2.1 Dose Modification and Toxicity Management for Immune-mediated AEs Associated with Pembrolizumab

AEs associated with pembrolizumab exposure may represent an immunologic etiology. These imAEs may occur shortly after the first dose or several months after the last dose of pembrolizumab treatment and may affect more than one body system simultaneously. Therefore, early recognition and initiation of treatment is critical to reduce complications. The dose of pembrolizumab should not be reduced. Based on existing clinical study data, most imAEs were reversible and could be managed with a delay of pembrolizumab, administration of corticosteroids and/or other supportive care. For suspected imAEs, ensure adequate evaluation to confirm etiology or exclude other causes. Additional procedures or tests such as bronchoscopy, endoscopy, skin biopsy may be included as part of the evaluation. Based on the severity of imAEs, withhold or permanently discontinue pembrolizumab and administer corticosteroids. Dose delay and toxicity management guidelines for imAEs associated with pembrolizumab are provided in [Table 9]. Participants who experience unacceptable toxicity that is clearly attributable only to enfortumab vedotin may continue on pembrolizumab monotherapy up to a maximum of 35 cycles.

Table 9 Dose Modification and Toxicity Management Guidelines for Immune-mediated AEs Associated with Pembrolizumab

General instructions:

1. Severe and life-threatening imAEs should be treated with IV corticosteroids followed by oral steroids. Other immunosuppressive treatment should begin if the imAEs are not controlled by corticosteroids.
2. Pembrolizumab must be permanently discontinued if the imAE does not resolve or the corticosteroid dose is not ≤ 10 mg/day within 12 weeks of the last pembrolizumab treatment.
3. The corticosteroid taper should begin when the imAE is \leq grade 1 and continue at least 4 weeks.
4. If pembrolizumab has been withheld, pembrolizumab may resume after the imAE decreased to \leq grade 1 after corticosteroid taper.

Immune-mediated AEs	Toxicity grade (NCI-CTCAE V5.0)	Action with Pembrolizumab	imAE Management with Corticosteroid and/or Other Therapies	Monitoring and Follow-up
Pneumonitis	Grade 2 Recurrent grade 2, grade 3 or grade 4	Withhold Permanently discontinue	
 Administer corticosteroids (initial dose of 1 to 2 mg/kg prednisone or equivalent) followed by taper Add prophylactic antibiotics for opportunistic infections 	
 Monitor subjects for signs and symptoms of pneumonitis Evaluate subjects with suspected pneumonitis with radiographic imaging and initiate corticosteroid treatment
Diarrhea / Colitis	Grade 2 or 3 Recurrent grade 3 or grade 4	Withhold Permanently discontinue	Administer corticosteroids (initial dose of 1 to 2 mg/kg prednisone or equivalent) followed by taper	
 Monitor subjects for signs and symptoms of enterocolitis (i.e., diarrhea, abdominal pain, blood or mucus in stool with or without fever) and of bowel perforation (i.e., peritoneal signs and ileus) Subjects with grade ≥ 2 diarrhea suspecting colitis should consider GI consultation and performing endoscopy to rule out colitis Subjects with diarrhea/colitis should be advised to drink liberal quantities of clear fluids. If sufficient oral fluid intake is not feasible, fluid and electrolytes should be substituted via IV infusion

Immune-mediated AEs	Toxicity grade (NCI-CTCAE V5.0)	Action with Pembrolizumab	imAE Management with Corticosteroid and/or Other Therapies	Monitoring and Follow-up
AST, ALT elevation or Increased bilirubin	Grade 2 ^a	Withhold	Administer corticosteroids (initial dose of 0.5 to 1 mg/kg prednisone or equivalent) followed by taper	Monitor subjects with liver function tests (consider weekly or more frequently until liver enzyme value returned to baseline or is stable)
	Grade 3 ^b or 4 ^c	Permanently discontinue	Administer corticosteroids (initial dose of 1 to 2 mg/kg prednisone or equivalent) followed by taper	
T1DM or Hyperglycemia	New onset T1DM or grade 3 or 4 hyperglycemia associated with evidence of β -cell failure	Withhold ^d	
 Initiate insulin replacement therapy for subjects with T1DM Administer antihyperglycemic in subjects with hyperglycemia 	Monitor subjects for hyperglycemia or other signs and symptoms of diabetes
Hypophysitis	Grade 2 Grade 3 or 4	Withhold Withhold or permanently discontinue ^d	Administer corticosteroids and initiate hormonal replacements as clinically indicated	Monitor subjects for signs and symptoms of hypophysitis (including hypopituitarism and adrenal insufficiency)
Hyperthyroidism	Grade 2 Grade 3 or 4	Continue Withhold or permanently discontinue ^d	Treat with nonselective beta-blockers (e.g., propranolol) or thionamides as appropriate	Monitor for signs and symptoms of thyroid disorders
Hypothyroidism	Grade 2 Grade 3 or 4	Continue Withhold or permanently discontinue	Initiate thyroid replacement hormones (e.g., levothyroxine or liothyronine) per standard of care	Monitor for signs and symptoms of thyroid disorders
Nephritis: grading according to increased creatinine or acute kidney injury	Grade 2 Grade 3 or 4	Withhold Permanently discontinue	Administer corticosteroids (prednisone 1 to 2 mg/kg or equivalent) followed by taper	Monitor changes of renal function

Immune-mediated AEs	Toxicity grade (NCI-CTCAE V5.0)	Action with Pembrolizumab	imAE Management with Corticosteroid and/or Other Therapies	Monitoring and Follow-up
Neurological Toxicities	Grade 2 Grade 3 or 4	Withhold Permanently discontinue	Based on severity of AE administer corticosteroids	Ensure adequate evaluation to confirm etiology and/or exclude other causes
Myocarditis	Asymptomatic cardiac enzyme elevation with clinical suspicion of myocarditis (previously CTCAE v4.0 Grade 1) Grade 2, 3 or 4	Withhold Permanently discontinue	Based on severity of AE administer corticosteroids	Ensure adequate evaluation to confirm etiology and/or exclude other causes
Exfoliative Dermatologic Conditions	Suspected SJS, TEN or DRESS Confirmed SJS, TEN or DRESS	Withhold Permanently discontinue	Based on severity of AE administer corticosteroids	Ensure adequate evaluation to confirm etiology or exclude other causes
All Other Immune-mediated AEs	Persistent grade 2 Grade 3 Recurrent grade 3 or 4	Withhold Withhold or discontinue based on the event ^e Permanently discontinue	Based on severity of AE administer corticosteroids	Ensure adequate evaluation to confirm etiology or exclude other causes

AE(s): adverse event(s); ALT: alanine aminotransferase; AST: aspartate aminotransferase; CTCAE: Common Terminology Criteria for Adverse Events; DRESS: Drug Rash with Eosinophilia and Systemic Symptom; GI: gastrointestinal; imAE: immune-related adverse event; IV: intravenous; NCI-CTCAE: National Cancer Institute Common Terminology Criteria for Adverse Events; SJS: Stevens-Johnson syndrome; T1DM: type 1 diabetes mellitus; TEN: toxic epidermal necrolysis; ULN: upper limit of normal.
 
Note: Non-imAE will be managed as appropriate, following clinical practice recommendations.
 
^a AST/ALT: > 3.0 to 5.0 × ULN if baseline normal; > 3.0 to 5.0 × baseline, if baseline abnormal; bilirubin: > 1.5 to 3.0 × ULN if baseline normal; > 1.5 to 3.0 × baseline if baseline abnormal
 
^b AST/ALT: > 5.0 to 20.0 × ULN, if baseline normal; > 5.0 to 20.0 × baseline, if baseline abnormal; bilirubin: > 3.0 to 10.0 × ULN if baseline normal; > 3.0 to 10.0 × baseline if baseline abnormal
 
^c AST/ALT: > 20.0 × ULN, if baseline normal; > 20.0 × baseline, if baseline abnormal; bilirubin: > 10.0 × ULN if baseline normal; > 10.0 × baseline if baseline abnormal
 
^d The decision to withhold or permanently discontinue pembrolizumab is at the discretion of the investigator or treating physician. If control achieved or ≤ grade 2, pembrolizumab may be resumed.
 
^e Events that require discontinuation include but are not limited to: encephalitis and other clinically important imAEs (e.g., vasculitis and sclerosing cholangitis).
				

